4.3 Withdrawal Criteria

Participation of a participant in this clinical study will be discontinued for any of the following reasons:

- Withdrawal of consent; or
- Termination of the study by the Sponsor or the regulatory authority.

Study drug treatment may be discontinued either permanently or temporarily (although the participant should be encouraged to remain in the study and to follow up for study visits) for any of the following reasons:

- Occurrence of any medical condition or circumstance that exposes the participant to substantial risk and/or does not allow the participant to adhere to the requirements of the protocol;
- Any serious AE (SAE), clinically significant AE, severe laboratory abnormality, intercurrent illness, or other medical condition which indicates to the Investigator that continued participation is not in the best interest of the participant;
- Requirement of prohibited concomitant medication;
- Pregnancy (permanent discontinuation of study drug); or
- Participant failure to comply with protocol requirements or study-related procedures.

Participants are free to withdraw consent from the study (which means permanent discontinuation of study drug and all follow-up assessments) at any time without prejudice. Note that discontinuation of study drug in and of itself is **not** considered withdrawal of consent.

Every attempt should be made to keep participants on study drug throughout the duration of the study. Before permanently discontinuing study drug (either participant- or Investigator-initiated), an interruption should be considered. Participants who temporarily discontinue study drug for any reason should restart as soon as it is medically justified in the opinion of the Investigator.

All participants who permanently discontinue study drug should continue scheduled study visits. In addition, all procedures and laboratory samples or tests requested for evaluation following administration of the study drug should be carried out when possible, whether or not a subject continues to receive treatment according to the protocol.

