For participants who permanently discontinue from study treatment **and who decline continued study participation**, an Early Termination (ET) Visit will be scheduled as soon as possible followed by an EOS Visit approximately 35 days later. The ET Visit procedures are identical to the End of Treatment (EOT) Visit procedures. If the discontinuation occurs at a specific onsite visit, this visit will become the ET Visit and EOT Visit procedures should be followed. Participants who withdraw consent to all follow-up will be asked about the reason(s) and will be assessed for the presence of any AEs.

If premature withdrawal from the study occurs for any reason, the Investigator must determine the primary reason for a participant's premature withdrawal from the study and record this information in the medical records and on the electronic case report form (eCRF).

Withdrawn participants will not be replaced.

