8.1 Adverse Events

An AE is defined as any untoward medical occurrence in a clinical investigation participant administered a pharmaceutical product, which does not necessarily have a causal relationship with this treatment. An AE can therefore be any unfavorable and/or unintended sign (including an abnormal laboratory finding), symptom, or disease temporally associated with the use of an investigational medicinal product, whether or not related to the investigational medicinal product. All AEs, including observed or volunteered problems, complaints, or symptoms, are to be recorded on the appropriate eCRF.

AEs, which include clinical laboratory test variables, will be monitored and documented from the time of signing of informed consent at Screening until the EOS Visit (approximately 35 days after the EOT Visit). Participants should be instructed to report any AE that they experience to the Investigator, whether or not they think the event is due to study treatment. Beginning at the time of signing of informed consent, Investigators should make an assessment for AEs at each visit and record the event on the appropriate AE eCRF.

Wherever possible, a specific disease or syndrome rather than individual associated signs and symptoms should be identified by the Investigator and recorded on the eCRF. However, if an observed or reported sign or symptom is not considered a component of a specific disease or syndrome by the Investigator, it should be recorded as a separate AE on the AE eCRF. Additionally, the condition that led to a medical or surgical procedure (eg, surgery, endoscopy, tooth extraction, or transfusion) should be recorded as an AE, not the procedure itself.

Any medical condition already present at Screening should be recorded as medical history and not be reported as an AE unless the medical condition or signs or symptoms present at Baseline change in severity, frequency, or seriousness at any time during the study. In this case, it should be reported as an AE.

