3.1.2 Analysis Visits

Scheduled visits will be assigned to analysis visits as recorded on the CRF.

For each analysis visit, if a scheduled visit occurs within the analysis day window, then the measurement from this scheduled visit will be used. If no scheduled visit occurs or laboratory results of the scheduled visit were unreportable, the unscheduled measurement closest to the target day will be used. If measurements are equidistant to the target day, the latter will be used. Otherwise, unscheduled visits will not be re-assigned and will remain labelled as unscheduled. If laboratory measurements for the scheduled visit were taken while a participant was not in a fasting state and laboratory measurements are available from an unscheduled visit during which the participant was in a fasting state (and the visit occurred within seven days of the scheduled visit), those fasted labs will be utilized in place of the unfasted labs.

Early termination (ET) visits will be assigned to analysis visits according to the following visit windows in Table 2:

Table 2 Analysis Visit Windows

Analysis Visit	Target Analysis Day	Low Analysis Day	High Analysis Day
Day 1 (Visit 2)	1	NA	NA
Day 30 (Visit 3)	30	2	57
Day 84 (Visit 4)	84	58	132
Day 180 (Visit 5)	180	133	225

Day 270 (Visit 6)	270	226	317
Day 365 (EOT)/(Visit 7)	365	318	N/A

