- A $>25\%$ decrease in eGFR from Baseline or an eGFR < 30 mL/min/1.73 m², calculated using the Chronic Kidney Disease Epidemiology Collaboration equation, and/or an increase in serum creatinine of ≥ 0.3 mg/dL (≥ 26.5 μ mol/L) from Baseline;
- Changes to antihypertensive medication(s) due to changes in blood pressure in those participants receiving antihypertensive medication(s) treatment at Baseline and those participants not receiving antihypertensive medication(s) treatment at Baseline; and
- Macular degeneration.

An overview of ESIs described above will be provided including counts, percentages of participants by treatment group, and a listing of each ESI.

Values and changes from baseline will be summarized for ALT, AST, and total bilirubin by visit and treatment group. The number and percent of participants with abnormal values for ALT, AST, and total bilirubin will be summarized. These summaries of participants with abnormal values will be performed overall; by normal Baseline; and by abnormal Baseline for ALT, AST, and total bilirubin individually. Hy's Law criteria ($>3 \times \text{ULN}$ for either ALT or AST, with accompanying total bilirubin $>2 \times \text{ULN}$) will also be applied to the data. Any potential Hy's Law cases will be listed separately.

Values and changes from Baseline will be summarized for CK levels by visit and treatment group and visit. In addition, the number and percent of participants with abnormal CK values will be summarized. These summaries of participants with abnormal CK values will be performed overall, by normal Baseline CK, and by abnormal Baseline CK. Values of CK from Baseline to EOT will be summarized by treatment group and by Baseline eGFR category.

Cases of NODM will be recorded and summarized using the appropriate system organ class. These events will be summarized by severity and relationship to study drug for each treatment group. Fasting plasma glucose and HbA1c will be monitored as specified in [Table 1 Schedule of Procedures](#).

Baseline eGFR will be summarized by treatment group for actual value and for Baseline eGFR categories. Shift tables of eGFR category from Baseline to EOT will be provided by treatment group. Shift tables of urine albumin-creatinine ratio and urine protein-creatinine ratio from Baseline to EOT will be provided by treatment group.

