Vital signs (heart rate and blood pressure) measured in triplicate prior to study administration at applicable visits as indicated in Table 1. Values will be summarized with descriptive statistics, including the change from Baseline at each visit by treatment group and overall.

Additional summaries of blood pressure measurements will be performed, within treatment group and time point, using counts of triplicate means that meet the following criteria:

- Systolic blood pressure:
 - ≥ 160 mmHg
 - ≥ 180 mmHg
 - change from Baseline by ≥ 20 mmHg
- Diastolic blood pressure:
 - ≥ 100 mmHg
 - ≥ 110 mmHg
 - change from Baseline by ≥ 15 mmHg.

As described above, the number and percentage of participants receiving antihypertensive medications at Baseline with changes to antihypertensive medications due to change in blood pressure will be summarized by treatment group. The number of participants who were not hypertensive or on any antihypertensive medications at Baseline, but started one or more antihypertensive drugs during the treatment period, will be summarized by treatment group.

Vital signs will be listed.

3.5.5 *Electrocardiograms*

A single 12-lead ECG will be performed at Visit 2 and Visit 7/EOT/ET and will be read locally.

ECG parameters will be recorded as normal, abnormal or not done. Abnormal values will be assessed as clinically significant or not clinically significant. Counts and percentages for ECG parameters will be summarized by treatment group and in total.

3.5.6 *Physical Examinations*

Physical examinations (with focused examination on general, respiratory, CV, abdominal, and extremities evaluations) and recording of weight and height will be performed at Screening Visit and Visit 7/EOT/ET. Height will be measured at Screening Visit only and used to calculate body mass index. BMI will be calculated as weight/(height/100)² (kg/m²); rounded and displayed to 1 decimal place.

Physical examination, parameters, will be recorded as normal, abnormal or not done. Abnormal values will be assessed as clinically significant or not clinically significant. Count and percentages for physical parameters will be summarized by treatment group and in total.

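### EOT safety tables pool off-drug with on-drug values, because participants who stop drug but stay in the study reach EOT at Day 365

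*SAP*

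**What the plan says.** **After a permanent stop.** Protocol 4.3 says "All participants who permanently discontinue study drug should continue scheduled study visits". The early visit is for a narrower group: "For participants who permanently discontinue from study treatment and who decline continued study participation, an Early Termination (ET) Visit will be scheduled". For that group, "The ET Visit procedures are identical to the End of Treatment (EOT) Visit procedures". The same paragraph adds: "If the discontinuation occurs at a specific onsite visit, this visit will become the ET Visit and EOT Visit procedures should be followed".

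**What EOT means in the analysis.** In SAP 3.1.2, the last row of Table 2 begins "Day 365 (EOT)/(Visit 7". Its target is Day 365, its lower limit Day 318, and it has no upper limit and no condition of being on drug. ET visits are allocated by these windows.

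**What is tabulated at EOT.**
- ECG (SAP 3.5.5): "A single 12-lead ECG will be performed at Visit 2 and Visit 7/EOT/ET and will be read locally".
- Physical examination (SAP 3.5.6): Screening and Visit 7/EOT/ET only.
- Renal (SAP 3.5.2): "Shift tables of eGFR category from Baseline to EOT will be provided by treatment group". UACR and UPCR are treated in the same way.
- General laboratory shifts (SAP 3.5.3): at the end of treatment visit. Protocol 9.2.2 has them at post-Baseline visits, in the plural. SAP Section 6 does not list this narrowing among its four changes.

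**When EOS falls.** Protocol 8.1 collects adverse events "until the EOS Visit (approximately 35 days after the EOT Visit". Protocol 3.1 and Appendix A instead place EOS 35 days after the last dose.

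**The concern.** The protocol rightly encourages participants who stop drug to stay. If they follow it, the visit labelled EOT is not at their end of treatment. A table headed Baseline to EOT will be read as showing the state at the end of exposure, yet for these participants it shows the state at Day 365.

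The renal tables are the most exposed to informative mixing. Protocol 8.1.4.4 makes a confirmed, unexplained creatinine or eGFR change a ground for discontinuing drug, so stopping is linked to the variable being tabulated. For the ECG the issue is simpler: there is one scheduled post-Baseline recording, and for a participant who stopped and stayed it is taken off drug.

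**Working it through.** **The plan's own figure.** Protocol 9.2.5 assumes 5% dropout: 300 × (1 − 0.05) = 285, which reproduces. This is loss from the study. It is not the rate of stopping drug while staying, and the documents give no such rate.

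**Time off drug at Visit 7** = 365 − day of stopping (nominal days, Appendix A):

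| Stop at | Days off drug at Day 365 |
|---|---|
| Day 30 | 365 − 30 = 335 |
| Day 84 | 365 − 84 = 281 |
| Day 180 | 365 − 180 = 185 |
| Day 270 | 365 − 270 = 95 |

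**Share of those who stop and stay that is long off drug at Visit 7.** Two assumed patterns of stopping:
- Uniform over 365 days, P(off > k) = 1 − k/365. For k = 35: 330/365 = 90%. For k = 90: 275/365 = 75%. For k = 180: 185/365 = 51%.
- Front-loaded: exponential with an 84-day half-life, truncated at Day 365, P(off > k) = (1 − 2^(−(365−k)/84)) / (1 − 2^(−365/84)). This gives 98%, 94% and 82%.

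**Number affected (assumed rates).** With 2:1 allocation of 300, 2% to 20% stopping and staying is 0.02 × 200 = 4 to 0.20 × 200 = 40 on obicetrapib, and 2 to 20 of 100 on placebo.

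**What the eGFR shift table loses, and what survives.** Take illustrative values of 80 at Baseline, 58 at Day 90 (confirmed, drug stopped) and 78 at Day 365. The fall is (80 − 58)/80 = 27.5%, above the 25% ESI threshold in Protocol 8.1.4, so the event is counted and listed. With the eGFR categories of SAP 3.3.4, both 80 and 78 lie in 60 to <90, so the Baseline-to-EOT table shows no shift.

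**EOT and EOS timing.** If a participant stops at Day 90 and stays, EOS counted from the last dose is Day 90 + 35 = 125, before Visit 5 at Day 180. Counted from EOT it is Day 365 + 35 = 400. The two rules agree only when EOT coincides with the last dose.

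**The case against.** **Other reporting covers much of this.** A reader might infer that recovered abnormalities are hidden. For eGFR and creatinine the documents do not support that. The full and limited panels together cover the treatment visits (Appendices A and B). Threshold changes are ESIs once confirmed, at any time after Randomization (Protocol 8.1.4 and 8.1.4.4). SAP 3.5.2 gives ESI counts, percentages and a listing. Macular degeneration is likewise an ESI in its own right, with no restriction to EOT. This stands, and it limits the eGFR loss to the shift tables. It does not cover UACR and UPCR, which are not ESI criteria.

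**ECG findings can be adverse events.** Protocol 8.1 captures clinically significant findings, but only if they are detected, and no scheduled on-drug ECG exists to detect them in these participants. A reader might also infer that those who stop for adverse events are the likeliest to have abnormal ECGs. The documents give no data for this, and Protocol 1.4 reports a thorough QT study with no effect on the Fridericia-corrected interval.

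**The meaning of EOT is not settled.** The sentence "If the discontinuation occurs at a specific onsite visit, this visit will become the ET Visit and EOT Visit procedures should be followed" stands among the rules for decliners but is not worded as limited to them. SAP 3.3.7 also uses an end of treatment date as a fallback for the last dose date. Day 365 is therefore the natural reading, not the only one. The ambiguity itself calls for a definition.

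**Decliners against stayers.** It is tempting to say that two participants stopping on the same day enter the EOT table on or off drug depending only on whether they decline visits. That is not safe. Under SAP 3.1.2 an ET visit before Day 318 maps to an earlier window, so the decliner's value may not enter a Day 365 summary at all.

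**Size.** No rate supports a claim that this happens often or that it materially dilutes a signal. Even at an assumed 20%, 80% of the arm is unaffected. Safety is descriptive, and the DSMB reviews unblinded ESIs about every six months (SAP 4).

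**Conclusion.** The point holds as a defect in the definition of the EOT safety tables. As written, they combine completers' on-drug values with Day 365 values from participants who stopped earlier and stayed. Given an early stop, the off-drug interval is long: 75% to 94% would be more than 90 days off drug under the two assumed stopping patterns. How many participants this concerns cannot be derived from the documents; 4 to 40 of 200 on obicetrapib is an assumed range.

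The consequence differs by measure. For eGFR it is confined to the shift tables. For UACR and UPCR, the EOT shift is the only summary that SAP 3.5.2 names. For the ECG, these participants have no scheduled on-drug post-Baseline recording, so an on-drug change that has resolved would not appear in the ECG summary. The conclusion rests on reading Visit 7/EOT as Day 365 for participants who stay.

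**What to change.** **SAP 3.5, analysis only.**
1. For the safety shift tables, define the EOT value as the last post-Baseline value taken on treatment or within a stated interval of last dose, for example 35 days. Include qualifying ET values whatever Table 2 window they fall in.
2. Add by-visit or worst post-Baseline shifts for eGFR, UACR and UPCR from samples already scheduled. This also brings the SAP back towards the post-Baseline visits of Protocol 9.2.2.
3. Show Visit 7 ECG and physical examination results obtained beyond that interval separately, as off treatment.

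**Cost.** One derived variable (days since last dose) and a little more programming, with no new data. Some early stoppers will have no qualifying EOT value, mainly for analytes drawn at few visits. For eGFR, UACR and UPCR this should be rare: Visit 3 falls by Day 33, at most 33 − 1 = 32 days after a last dose on Day 1.

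**For the sponsor to reconcile.** Protocol 4.3, 8.1 and Appendix A should agree on when EOT and EOS procedures take place for participants who stop drug and remain. No change to the timing of assessments is proposed here. Moving the ECG to the next scheduled visit, for instance, would not by itself secure a value within 35 days of last dose. The gaps between visits are 29, 54, 96, 90 and 95 days. With stops spread evenly between visits, (0 + 19 + 61 + 55 + 60)/364 = 54% would fall outside, and the Day 365 recording would be given up.

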4 DATA SAFETY MONITORING BOARD

An independent Data Safety Monitoring Board (DSMB) will monitor unblinded safety data, including blood pressure changes over time and the occurrence of ESIs during the study on a bi-annual basis (ie, approximately every 6 months). Participants, investigators, site staff and in general all personnel directly involved in the conduct of the study will remain blinded to the participants' treatment assignment until the completion of the study.

Details related to the DSMB responsibilities, authorities, and procedures will be documented in a DSMB Charter.

5 ANALYSIS TIMING

5.1 Interim Analysis

No interim analysis is planned.

5.2 Pre-Final Analysis

After the database is locked and exclusions from analysis populations have been finalized, the randomized treatment assignments will be unblinded and the pre-final analysis will be generated. Pre-final tables, figures, and listings (TFLs) will be provided approximately 3 weeks after database lock.

5.3 Final Analysis

After all comments on the pre-final analysis have been resolved and the study database is declared final, the final analysis will be generated. If there were no changes to the pre-final analysis or the study database, the pre-final TFLs may be considered final. In addition to TFLs, SDTM data and ADaM data along with associated files will be provided. Associated files may include annotated case report forms (CRFs), SDTM specifications, SDTM programs, ADaM

specifications, ADaM programs, TFL programs, and CDISC Define packages for both SDTM and ADaM data.

6 CHANGES FROM PROTOCOL-SPECIFIED STATISTICAL ANALYSES

There have been four changes from the protocol v3.0.

The first change is in the description of the study objectives and endpoints, the term 'fasting' from version 3.0 of the protocol, which precedes the specified lipid parameter, has been removed. The Schedule of Procedures, along with Section 8.7 of the protocol, specifies that all laboratory samples should be collected while the participant is fasting; therefore, the corresponding language was removed from the objective and endpoint descriptions in the SAP. Additionally, the primary efficacy endpoint for the LDL-C assessment will utilize values collected via preparative ultracentrifugation (PUC), also referred to as beta quantification, which is not sensitive to fasting status.

The second change is the inclusion of subgroup analysis.

The third change is the inclusion of the evaluation of trough levels of obicetrapib from Baseline to Day 84 and 180 in the obicetrapib group.

The fourth change is the change in the variance for the primary analysis. The model will assume unequal variances for each treatment group. Therefore, supportive analysis of the primary efficacy assessment will not require consideration of an ANCOVA model assuming unequal variances, as described in v3.0 of the protocol.

7 PROGRAMMING SPECIFICATIONS

Analyses will be performed using SAS® version 9.4 or higher. All available data will be presented in participant data listings which will be sorted by participant and visit date as applicable. Detailed Programming Specifications will be provided in a separate document.

APPENDIX B: PREFERRED TERMS FOR HYPERTENSION

Preferred Term
Accelerated hypertension
Blood pressure ambulatory increased
Blood pressure diastolic increased
Blood pressure inadequately controlled
Blood pressure increased
Blood pressure orthostatic increased
Blood pressure systolic increased
Diastolic hypertension
Essential hypertension
Hypertension
Malignant hypertension
Mean arterial pressure increased
Systolic hypertension
Blood pressure abnormal
Blood pressure ambulatory abnormal
Blood pressure diastolic abnormal
Blood pressure orthostatic abnormal
Blood pressure systolic abnormal
Labile blood pressure
Hypertensive crisis
Hypertensive emergency
Hypertensive urgency
Orthostatic hypertension
